### **5.1.3 Concomitant medication date imputation**

Impute CM end date:

1. If CM end day is missing and CM month/year are non-missing then impute CM day as the minimum of treatment end date and the last day of the month.
2. If CM end day/month are missing and CM year is non-missing then impute CM day as the minimum of treatment end date and the end of the year (31DECYYYY).
3. If imputed CM end date is less than the CM start date, use the CM start date as the imputed CM end date.

Impute CM start date:

1. If the CM start date year value is missing, the imputed CM start date is set to one day prior to treatment start date.
2. If the CM start date year value is less than the treatment start date year value, the CM started before treatment. Therefore:
  - a. If the CM month is missing, the imputed CM start date is set to the mid-year point (01JULYYYY).
  - b. Else if the CM month is not missing, the imputed CM start date is set to the mid-month point (15MONYYYY).
3. If the CM start date year value is greater than the treatment start date year value, the CM started after treatment. Therefore:
  - a. If the CM month is missing, the imputed CM start date is set to the year start point (01JANYYYY).
  - b. Else if the CM month is not missing, the imputed CM start date is set to the month start point (01MONYYYY).
4. If the CM start date year value is equal to the treatment start date year value:
  - a. And the CM month is missing or the CM month is equal to the treatment start date month, then the imputed CM start date is set to one day prior treatment start date.
  - b. Else if the CM month is less than the treatment start date month, the imputed CM start date is set to the mid-month point (15MONYYYY).
  - c. Else if the CM month is greater than the treatment start date month, the imputed CM start date is set to the month start point (01MONYYYY).

If complete (imputed) CM end date is available and the imputed CM start date is greater than the (imputed) CM end date, then imputed CM start date should be set to the (imputed) CM end date.

#### **5.1.4 Medical history date imputation**

1. If the medical history date day/ month are missing and the year is non-missing:
  - a. If the year part of the date is equal to the year part of the inform consent date, then the imputed date is set to the year start point (01JANYYYY).
  - b. Otherwise the imputed date is set to the mid-year point (01JULYYYY).
2. If the medical history day is missing and the month/year are non-missing:
  - a. If the month and year part of date is equal to the month and year part of the inform consent date, then the imputed date is set to the month start point (01MONYYYY).
  - b. Otherwise the imputed date is set to the mid-month point (15MONYYYY).

#### **5.1.5 Other imputations**

For laboratory test values below Lower Level of Quantification (LLQ) or above Upper Level of Quantification (ULQ) will be imputed as LLQ or ULQ value, respectively. The numerical part of the reported result will be treated as the actual LLQ or ULQ. These laboratory values will be displayed in listings using the standard unit with the reported sign (“<” or “>”).

### **5.2 AEs coding/grading**

AEs will be coded according to MedDRA dictionary. The MedDRA version used for reporting the adverse events will be described in a footnote.

### **5.3 Laboratory parameters derivations**

The following criteria will be used to define expanded limits and clinically notable abnormalities of key laboratory tests.

#### **Liver Function and Related Variables**

Alanine transaminase (ALT) (SGPT):  $> 3 \times$  Upper Limit of Normal (ULN)

Aspartate transaminase (AST) (SGOT):  $> 3 \times$  ULN

Total bilirubin:  $> 2 \times$  ULN

Alkaline phosphatase:  $> 2.5 \times$  ULN

#### **Renal Function**

Creatinine (serum):  $> 1.5 \times$  ULN

## **Hematology**

Hemoglobin:  $\geq 20$  g/l decrease from baseline

Platelet count:  $<$  Lower Limit of Normal (LLN)

White blood cell count:  $< 0.8 \times$  LLN

Neutrophils:  $< 0.9 \times$  LLN

Eosinophils:  $> 1.1 \times$  ULN

Lymphocytes:  $> 1.1 \times$  ULN

## **5.4 Estimand Charter**

### **5.4.1 Introduction**

Secukinumab is being explored as a treatment for lichen planus, and studied in subjects with biopsy-proven forms of lichen planus not adequately controlled with topical therapies in the proof of concept trial CAIN457S12201.

This section describes the estimands and corresponding estimation procedures for the primary endpoint, in line with the latest discussions of the forthcoming ICH E9 (R1) addendum.

An estimand defines in detail what needs to be estimated to address a specific scientific question of interest. A description of an estimand includes five attributes:

- The population, that is, the patients targeted by the scientific question;
- The variable (or endpoint), to be obtained for each patient, that is required to address the scientific question;
- The treatment of interest. The test treatment of interest and the control treatment to which comparison will be made (if applicable).
- The specification of how to account for intercurrent events to reflect the scientific question of interest;
- The population-level summary for the variable that provides, as required, a basis for a comparison between treatment conditions.

This section focuses in particular on the management of intercurrent events (for example, discontinuation of assigned treatment, use of an additional or alternative therapy). Other aspects of the estimand like the population, the variable, the treatment of interest and the population-level summary for the variable are presented, but are not the focus of this document.

#### **5.4.1.1 Purpose of the CAIN457S12201 study**

The purpose of this proof of concept study is to explore the efficacy of secukinumab in the treatment of adult patients with biopsy-proven lichen planus not adequately controlled with topical therapies, and to assess the safety and tolerability over 32 weeks. The primary objective

of the study is to demonstrate the efficacy of secukinumab (300 mg Q4W) with respect to IGA response (i.e., achievement of IGA score  $\leq 2$ ) after 16 weeks of treatment compared to placebo.

#### 5.4.1.2 Different types of intercurrent events

[figure not shown]
[figure not shown]
1. Changes in the dose of allowed concomitant medications for topical therapy: patients entering the trial are not allowed to use any topical therapies except for the allowed concomitant topical medications (described in Section 6.2.1 of the protocol). Patients must have reached a stable dose and application frequency of these allowed topical treatments at least 2 weeks prior to randomization and the administration should remain stable regarding dose and application frequency during first 16 weeks treatment.
2. Other concomitant medications: medications that are not explicitly prohibited by the protocol (e.g., antibiotics or NSAIDs, or supplements).
3. Prohibited medications: medications that are prohibited by the protocol (described in Section 6.2.2 of the protocol) and that have a potential confounding effect on the efficacy of secukinumab (e.g. immunosuppressive agents such as methotrexate, cyclosporin or systemic glucocorticoids).
4. Discontinuation of study treatment.

A horizontal bar chart with 10 bars. The bars are black with white outlines. The lengths of the bars decrease from left to right. The first bar is the longest, followed by a very short bar, then a long bar, then a medium bar, then a very short bar, then a long bar, then a medium bar, then a very short bar, then a long bar, and finally a very short bar. The bars are set against a white background with a light gray horizontal grid.

[figure not shown]

[figure not shown]

[figure not shown]

[figure not shown]

[figure not shown]
A large black rectangular redaction box covers the majority of the page content, starting below the header and ending above the footer. The redaction is irregular, with some white space visible at the top and bottom edges.

[figure not shown]

[figure not shown]

[figure not shown]

[figure not shown]

[figure not shown]

[figure not shown]

[figure not shown]

[figure not shown]

[figure not shown]

A horizontal bar chart with 10 bars of varying lengths. The bars are black on a white background. The first bar is the longest, followed by the second, and then the third. The fourth bar is shorter than the first three. The fifth bar is the second shortest. The sixth bar is longer than the fourth and fifth bars. The seventh bar is longer than the fifth and sixth bars. The eighth bar is longer than the sixth and seventh bars. The ninth bar is shorter than the eighth bar. The tenth bar is the shortest of all.

## 5.6 Rule of exclusion criteria of analysis sets

**Table 5-18 Subject Classification**

Analysis Set	PD ID that cause subjects to be excluded	Non-PD criteria that cause subjects to be excluded
RAN	INCL01* M-INCL05-randomized in error	Not randomized
FAS	INCL01*	Not in RAN; Mis-randomized subjects
SAF	INCL01*	No study drug taken

\*Written informed consent must be obtained before any assessment is performed.

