## **2.2 Analysis sets**

The following analysis sets will be used for the data analysis. Rules of exclusion criteria of analysis are detailed in [Section 5.6](#).

The **Randomized Analysis Set (RAS)** consists of all randomized subjects. Subjects will be analyzed according to the treatment assigned at randomization.

The **Full Analysis Set (FAS)** comprises all subjects to whom study treatment has been assigned. Subjects will be analyzed according to the treatment assigned to at randomization. Mis-randomized subjects (mis-randomized in IRT) will be excluded from FAS. Mis-randomized subjects are defined as cases where IRT contacts were made by the site either prematurely or

inappropriately prior to confirmation of the subject's final randomization eligibility and no study medication was administered to the subject.

The **Safety Set** includes all subjects who received at least one dose of study treatment. Subjects will be analyzed according to the study treatment received, where treatment received is defined as the randomized/assigned treatment if the subject took at least one dose of that treatment or the first treatment received if the randomized/assigned treatment was never received.

The summary statistics analyses in this study will be performed according to domains with respective specifications of analyses sets, analyses period and treatment groups ([Table 2-1](#)).

**Table 2-1** Summary statistics specifications

Domains	Analyses sets	Analysis Period	Treatment group labels for each analysis period
Patient disposition, Demographics, Other baseline characteristics *	RAS	Treatment Period 1	Secukinumab 300 mg Q4W Placebo Total
		Treatment Period 2 Follow up (only for disposition tables)	Secukinumab 300 mg Q4W Secukinumab 300 mg Q2W Total
Efficacy endpoints	FAS	Treatment Period 1	Secukinumab 300 mg Q4W Placebo
		Entire treatment period	Secukinumab 300 mg Q4W Placebo Placebo-Secukinumab 300 mg Q2W
Safety data (Number of doses, duration of exposure, prior and concomitant therapies, concomitant medical procedures, significant non-drug therapies, laboratory data, AEs, etc.)	Safety set	Treatment Period 1	Secukinumab 300 mg Q4W Placebo
		Entire treatment period	Secukinumab 300 mg Q4W Secukinumab 300 mg Q2W Placebo Any Secukinumab

\* Treatment groups for protocol deviations for entire treatment period: AIN457 300 mg Q4W, AIN457 300 mg Q2W, Any AIN457 300 mg, Placebo, Total

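### SAP Table 5-18 excludes subjects coded as randomized in error from the Randomized set, against its definition, and as written carries the exclusion into the primary FAS with no dosing condition

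*SAP*

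**What the plan says.** SAP 2.2 and protocol 12.1 define the sets in the same terms.

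- The Randomized Analysis Set "consists of all randomized subjects". No exception is given.
- The FAS "comprises all subjects to whom study treatment has been assigned". The one stated exclusion is mis-randomized subjects: the site contacted the IRT too early or wrongly, before eligibility was confirmed, "and no study medication was administered to the subject".

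SAP 2.2 refers to SAP 5.6 for the exclusion rules. Table 5-18 there gives three rows:

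- **RAN:** excluded for missing consent (INCL01), for "M-INCL05-randomized in error", or if not randomized.
- **FAS:** excluded for INCL01, or under "Not in RAN; Mis-randomized subjects".
- **SAF:** excluded for INCL01, or under "No study drug taken". The randomized-in-error code is not listed.

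The SAP change history records that Amendment 1 added this deviation in order to take subjects out of the Randomized set, so the entry is deliberate. SAP 2.5.1 bases the primary endpoint on the FAS, separately in each cohort. SAP 2.3 bases disposition and baseline tables on the randomized set.

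**The concern.** A set defined as everyone randomized cannot also exclude randomized subjects by deviation code. That conflict stands whatever the code means, and it affects the accounting of who entered the trial: a subject with the code would be missing from the disposition and baseline tables.

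The second step could matter more. The FAS inherits every exclusion from the Randomized set, and Table 5-18 attaches no dosing condition to the code. If a subject was dosed and assessed and then given the code, a programmer following the table would drop that subject from the primary analysis but keep the subject in the Safety Set. That is a post-randomization exclusion which the FAS definition does not allow. In cohorts of 24 and 12, one subject can decide whether the criteria are met.

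**Working it through.** **1. Set membership, definitions against table.**

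| Randomized subject | RAS, SAP 2.2 | RAN, Table 5-18 | FAS, SAP 2.2 | FAS, Table 5-18 |
|---|---|---|---|---|
| Has the code, undosed, meets the mis-randomized definition | in | out | out | out |
| Has the code, dosed (if this can occur) | in | out | in | out |

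The Randomized-set columns disagree in both rows. The FAS columns disagree only in the second.

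**2. Inputs for the size of the effect.** 24 secukinumab and 12 placebo per cohort (SAP 1.1). Prior Beta(1/3, 1/3) in each arm, and success if Pr(δ > 0 | data) > 0.90 and Pr(δ > 0.15 | data) > 0.50 (SAP 2.5.2). Response rates are taken from SAP Table 3-1.

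**3. Method.** With s responders among n, the posterior is Beta(1/3 + s, 1/3 + n − s). Both posterior probabilities were found by numerical integration for all 25 × 13 = 325 outcomes and weighted by their binomial probabilities.

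**4. The plan's own figure.** At 50% v 20% this gives 0.712, matching the 71% in SAP 3. Ten scenarios of Table 3-1 were checked, at both 24:12 and 18:18, and all agree to three decimals.

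**5. Lose one subject at random.** The decision was recomputed at 24:11 or 23:12 for each outcome. The lost subject is a responder with probability s/n. Brackets show changes to success / to failure, in percentage points.

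| True rates | Success at 24:12 | One placebo lost: decision changes | Success at 24:11 | One active lost: decision changes | Success at 23:12 |
|---|---|---|---|---|---|
| 50% v 20% | 0.712 | 6.5% (3.5 / 3.0) | 0.716 | 3.9% (3.1 / 0.8) | 0.735 |
| 40% v 20% | 0.503 | 7.8% (3.7 / 4.1) | 0.499 | 4.8% (3.1 / 1.7) | 0.516 |
| 60% v 30% | 0.675 | 8.0% (3.8 / 4.2) | 0.671 | 3.6% (3.4 / 0.2) | 0.708 |

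For example, 0.712 + 0.035 − 0.030 gives 0.716 from unrounded values. With 20% in both arms, the chance of a false success is 0.087 at 24:12, 0.095 at 24:11 and 0.120 at 23:12. Changes after losing an active subject lean towards success because the outcomes are discrete and the rule at 23:12 is slightly easier to meet. Any loss of one active subject would do the same.

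**6. Single outcomes near the boundary.**

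- 9/24 v 2/12 succeeds: Pr(δ > 0) = 0.909, Pr(δ > 0.15) = 0.640. Without one placebo non-responder (9/24 v 2/11), Pr(δ > 0) is 0.883 and it fails.
- 11/24 v 3/12 fails: 0.893 and 0.631. Without one placebo responder (11/24 v 2/11), Pr(δ > 0) is 0.950 and it succeeds.

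**The case against.** The strongest reply is that the code may be only the deviation-list name for the mis-randomized group. The wording is close, the definition of that group requires that the subject "and no study medication was administered to the subject", and SAP 2.2 states this condition before referring to 5.6. The code is not defined in the available text, and protocol 5.1 lists only four inclusion criteria, so its definition must lie elsewhere. The Safety Set row fits this reading too, because undosed subjects already fall under "No study drug taken". If so, the FAS is what its definition says and the primary analysis is unaffected. This reply stands as a possibility. It does not remove the conflict over the Randomized set.

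Three stronger readings are tempting, and the documents do not support them.

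- A reader might infer that the code must reach beyond undosed subjects, since the FAS row names mis-randomized subjects separately. The table repeats itself elsewhere: INCL01 is in the RAN row and again in the FAS row, although being outside RAN already covers it. A repeated entry therefore does not show a wider group.
- A reader might infer that the code will be assigned with treatment and outcome known. No process or timing for assigning it is described. Protocol 6.4 keeps the trial team blind until database lock, with listed exceptions that include designated staff for the primary endpoint analysis. The text neither describes nor rules out later coding.
- A reader might take the share of changed decisions as bias. If the lost subject is assumed to be a placebo responder, 11 to 19% of decisions change, but nothing suggests that the code selects such subjects. The figures show how far a 24:12 cohort depends on any one subject.

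**Conclusion.** The concern holds in two parts of different strength. The contradiction over the Randomized set is certain: it follows from the wording of SAP 2.2, protocol 12.1 and Table 5-18, and it reaches the disposition and baseline tables. The effect on the primary FAS is conditional. As written, the table would remove any dosed subject given the code, contrary to the FAS definition, but the documents do not show that a dosed subject can receive it, and they give no count.

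If one such subject exists in a cohort and is unrelated to outcome, the decision changes in about 6 to 8% of trials for a placebo subject and about 4 to 5% for an active subject, in both directions. The average success probability shifts by at most 0.004 for a placebo subject and 0.033 for an active subject at these scenarios. This is a specification error that should be corrected, not a demonstrated bias.

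**What to change.** In SAP Table 5-18, delete the randomized-in-error code from the RAN row. For the FAS, rely on the existing mis-randomized criterion, with its condition that no study medication was given. Define the code in the SAP. State that any dosed subject who carries it stays in the RAS and FAS and is reported as a protocol deviation. A sensitivity analysis without such subjects is optional.

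The cost is one table row and a sentence or two. The consent exclusion need not change, and the definitions in SAP 2.2 and protocol 12.1 can stay as they are. The downside is that a few ineligible but dosed subjects may stay in the primary analysis.

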## 5.7 Descriptions of some efficacy endpoints

### 5.7.1 Investigator's Global Assessment grading (IGA)

**Table 5-19 IGA**

IGA score	Cutaneous Lichen Planus	Mucosal Lichen Planus	Lichen Planopilaris
0 - Clear	No disease. Possible flat, hyperpigmented lesions.	No disease.	No active disease. Hypopigmented, cicatricial patches. Pull test negative.

1 - Minimal	Barely palpable (<0.5 mm), scattered papules, mild erythema. Typically associated with minimal pruritus.	Reticular, white, patch-type striations involving any oral or genital mucosal site(s) ("Wickham Striae"). Absence of ulcers. Typically associated with no symptoms.	Predominantly inactive disease (hypopigmented cicatricial patches). Absence of disease spreading. Pull test negative. Minimal scalp erythema and/or perifollicular erythema without scale. Typically associated with minimal pruritus.
2 - Mild	Moderately elevated papules (<1 mm) and/or small plaques (<2 cm  ). Involvement of limited areas, erythema. Typically associated with mild pruritus.	Plaque-type, mucosal lichen planus involving any oral or genital mucosal site(s). Absence of ulcers or presence of one focal ulceration (<0.5 cm  ). Typically associated with mild pain or sensitivity.	Rare perifollicular erythema, rare perifollicular hyperkeratosis and interfollicular scale. Stable or slowly spreading disease. Pull test negative. Typically associated with mild pruritus.
3 - Moderate	Thick, elevated (<2 mm), hypertrophic, violaceous papules or presence of non-hypertrophic, plaque-like disease (>2 cm  ), either generalized or involving specific areas or specific locations (e.g. face, neck). Red/violaceous erythema, possible scales. Typically associated with moderate pruritus.	Desquamative gingivitis or vulvitis. Presence of unilateral or bilateral ulcerations involving any oral or genital mucosal site(s). Overall area affected by ulceration should be <2 cm  . Typically associated with moderate pain and sensitivity.	Hairless patches with perifollicular and interfollicular erythema, follicular hyperkeratosis and interfollicular scaling. Active spreading disease. Pull test positive for telogen hairs. Typically associated with moderate pruritus, pain and/or burning.
4 - Severe	Generalized, papular or plaque-type, elevated lesions (>2 mm) OR localized hypertrophic lesions (>2 cm  ). Marked red/violaceous erythema. Possible scales, blisters and ulcers. Typically associated with severe pruritus.	Presence of bilateral or extensive unilateral ulcers involving any oral or genital mucosal site(s). Overall area affected by ulceration should be >2 cm  . Possible esophageal involvement (established by endoscopy). Typically associated with severe pain and sensitivity.	Hairless patches with perifollicular and interfollicular, intense erythema, extensive perifollicular and interfollicular scaling. Crusting, pustules. Active spreading disease. Pull test positive for telogen or anagen hairs. Typically associated with severe pruritus, pain and/or burning.

**The grading should be mainly driven by the lesion characteristics.** Symptoms, such as pain

or pruritus, may or may not be associated.

### **5.7.2 Patient Assessment of Itch (NRS)**

Itch is assessed with the following questions:

- "Overall, how severe was your lichen planus-related itching during the past 24 hours?"
- "How severe was your lichen planus-related itching **at the worst moment** during the past 24 hours?"
- "Overall, how bothered were you by your lichen planus-related itching during the past 24 hours?"

Answers are given on a numeric rating scale (NRS). The Patient Assessment of Itch will be assessed on all subjects.

### **5.7.3 Patient Assessment of Pain (NRS)**

Pain is assessed with the following questions:

- "Overall, how severe was your lichen planus-related pain during the past 24 hours?"
- "How severe was your lichen planus-related pain **at the worst moment** during the past 24 hours?"
- "Overall, how bothered were you by your lichen planus-related pain during the past 24 hours?"

Answers are given on a numeric rating scale (NRS). The Patient Assessment of Pain will be assessed on all subjects.

### **5.7.4 Physician's assessment of surface area of disease (PSAD)**

Assessment scores range from 0-5, with lower scores corresponding to lower percentages of surface area with disease.

**0:** clear

**1:** <2% of the total body surface area. Small, localized papules

**2:** 2-9% of the total body surface area. Lesions affecting limited areas (e.g. wrists or ankles)

**3:** 10-29% of the total body surface area. Lesions affecting extensive areas (e.g. upper limbs or back)

**4:** 30-50% of the total body surface area. Lesions affecting extensive areas or in multiple locations (e.g. trunk and lower/upper limbs)

**5:** >50% of the total body surface area. Generalized involvement

*As reference, the percentages utilized for the Body Surface Area (BSA) assessment should be considered (head=10%, trunk=30%, upper limbs=20%, lower limbs=40%).*

